4.4 Co-Enrollment Considerations

Co-enrollment in this study and other studies is permitted without prior approval of the Protocol Team, as long as requirements of both studies can safely be met and blood draw maximums will

not be exceeded (see Section 6.8.1). All investigational agents must be documented as concomitant medications (see Section 5.3).

4.5 Recruitment, Screening, and Enrollment Process

RDV is an approved drug for treatment of COVID-19 in adults and pediatric patients requiring hospitalization, who are 12 years of age or older and who weigh at least 40 kg. Recruitment methods for this study may vary across sites but are expected to rely on identification of pregnant and non-pregnant women hospitalized for COVID-19 in a facility that is affiliated with an IMPAACT clinical research site and who recently initiated treatment with RDV or who may require treatment with RDV. Clinical research site staff will work with local care providers to identify hospitalized pregnant and non-pregnant women with COVID-19.

Due to COVID-19 infection control measures, hospitalized pregnant and non-pregnant women are expected to be in isolation. Additionally, participants may be incapacitated and determined, per site-specific SOPs and sIRB or other institutional, state, or local guidelines, to be unable to provide independent consent for themselves. Site staff must ensure that information about the study is provided to the potential participant or her LAR (as applicable) including detailed review of the study informed consent form, time to address any questions or concerns the potential participant or LAR may have, and an assessment of understanding, before proceeding to informed consent decision. Refer to Section 13.3 for further information on informed consent procedures for this study, including allowable consenting options in the context of COVID-19. The informed consent process will be conducted in accordance with sIRB and other institutional and local policies and procedures, and fully documented consistent with the NIAID DAIDS policies referenced in Section 11.2 and with 45 CFR 46.117.

Eligibility screening will be initiated after informed consent is provided. Screening evaluations must be completed prior to enrollment. Screening evaluations may be performed up to and on the day of enrollment; however, all required screening outcomes must be available prior to enrollment.

Each site must establish SOPs for eligibility determination that describe where and when screening procedures will be performed; roles and responsibilities for performing the required procedures; roles and responsibilities for assessing and confirming eligibility; and procedures for documenting the process, taking into consideration the required timing of entry.

Prior to enrollment, and after informed consent is obtained, sites will assign a participant identification number (PID) to the participant. The IMPAACT Data Management Center (DMC) Subject Enrollment System (SES) will be used to enroll participants in this study. For women found to be eligible, enrollment will occur upon successful entry of required eligibility data into the SES. Successful entry into the SES will generate a study identification number (SID), for each enrolled participant. Refer to Section 9.5 for more information on monitoring participant accrual in this study.

For Arm 1, only maternal participants will be enrolled in the study; fetuses/infants will not be enrolled. However, as some limited data will be collected on infant outcomes at birth as well as newborn physical exam findings, participants will be asked to provide consent for data collection on their infants, as described in the sample consent forms in Appendix II. PIDs will not be assigned to infants and these data will be collected on maternal eCRFs.

4.6 Participant Retention

Once a participant is enrolled in this study, study staff will make every effort to retain her for the protocol-specified duration of follow-up, thereby maximizing evaluability and statistical power and minimizing potential biases associated with loss to follow-up. Study sites are responsible for developing and implementing local procedures to reach this goal. Refer to Section 9.5 for more information on monitoring participant retention in this study.

4.7 Participant Withdrawal or Discontinuation from the Study

Regardless of the participant retention procedures referenced above, participants or their LAR may voluntarily withdraw from the study. Participants may also be discontinued from study participation by the site investigator or designee under the following circumstances:

- Investigator or designee determines that continued participation in the study would be unsafe or otherwise not in the best interest of the participant, after consultation with the Clinical Management Committee (CMC).
- The study is stopped or canceled by the sponsors, government or regulatory authorities, or the sIRB.
- Site participation in the study is cancelled by the sponsors, government or regulatory authorities, or the sIRB.
- The participant does not initiate RDV within 7 days from study entry.

For any participant who withdraws or is discontinued from the study prior to scheduled completion of follow-up, study staff will document the reason for the withdrawal or discontinuation in detail and enter the reason into the appropriate eCRF. No final evaluations are required in the case of early study discontinuation or withdrawal.

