2 OBJECTIVES

2.1 Primary Objectives

The primary objectives of this study are to:

- **2.1.1** Arm 1: Describe the pharmacokinetics of RDV and its metabolite, GS-441524, after administration to pregnant women as part of clinical care.
- 2.1.2 Arm 1: Describe the clinical and laboratory safety outcomes through four weeks post-last infusion and during delivery in pregnant women receiving RDV as part of clinical care.

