6 STUDY PROCEDURES AND DATA COLLECTION REQUIREMENTS

An overview of study procedures including PK sampling, blood volumes and data collection requirements are presented in the Schedule of Evaluations (SOE) in Appendix I. Presented in this section is additional information on study procedures and data collection requirements for each study period as follows: baseline, infusion, safety-follow-up, and delivery (for women enrolled in Arm 1).

Because study participants will be hospitalized with COVID-19 at study entry and while receiving RDV infusions, and given COVID-19 infection control measures, IMPAACT 2032 study staff are expected to have limited contact with study participants. The treating physician (not affiliated with the study) is responsible for RDV management and clinical care. Study procedures for this study are limited to data collection and blood specimens for PK. The study procedures described in this section are the responsibility of the IMPAACT 2032 study staff. With the exception of PK sampling, study procedures will largely be done via medical chart abstraction and/or remote contact or telemedicine visit. Refer to Section 10 for more details on PK design and analysis. Refer to the IMPAACT 2032 Laboratory Processing Chart (LPC) for collection, processing, and shipping instructions for PK samples.

All procedures must be performed at the approved clinical research site or approved associated facilities. All procedures must be documented in accordance with the DAIDS policies for source documentation; refer to Section 11 for more information on documentation requirements and entry of eCRFs. Refer to Section 7 for information on expedited adverse event (EAE) reporting, which may be required at any time during follow-up.

In addition to the protocol-specified procedures described in this section and the SOE Appendix, study staff may complete other tasks consistent with site SOPs, including but not limited to collecting, reviewing, and updating demographic and locator information; reviewing elements of informed consent; and providing instructions for contacting study staff. All such tasks should be documented consistent with site SOPs.

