6.1 Data Collection Requirements

Collection of clinical and laboratory data is required throughout the study beginning at 48 hours before the first infusion and continuing through 4 weeks after the last infusion. Additionally, data will be collected at the time of delivery for participants in Arm 1, and limited data will also be collected from the birth and newborn exam records of their infants. The specific data collection requirements are described in each sub-section below specific to each time period. All information should be obtained based on available medical records or remote or telemedicine visit, in order to minimize physical contact with the participant. Data abstraction and reporting should be targeted to occur as close as possible to the data collection timepoint indicated in the SOE; for the infusion time period in particular, sites are encouraged to key data each day that infusions are administered, if possible.

Documented medical conditions will be assessed for severity as described in Section 7.2.1, and new conditions occurring after infusions begin will also be assessed for relationship to RDV as described in Section 8. Relevant dates will be recorded for all conditions and medications.

Abnormal findings identified prior to initiation of RDV infusions will be entered into medical history eCRFs, and abnormal findings identified after initiation of RDV infusions will be entered into adverse events eCRFs. Administration of RDV will be recorded on an Infusion Treatment Log eCRF and use of concomitant medications in the time periods specified below will be recorded on the Concomitant Medication Log eCRF. Laboratory test results will be recorded on laboratory eCRFs as specified in Section 6.

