6.7 Early Discontinuation of Remdesivir

Women who discontinue RDV after initial PK sampling but prior to the 5th infusion will have no further PK sampling done. These women will be followed for safety and clinical outcomes throughout the duration of the study follow-up period, and clinical and laboratory data will continue to be collected as indicated in the SOE.

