The intracellular concentrations of GS-443902 at each timepoint and in each arm will be summarized using descriptive statistics and compared between pregnant and non-pregnant women using the GMR with a 90% CI. Individual-level concentrations over time will also be visualized using spaghetti plots and compared within individual.

The RDV free fraction from *ex vivo* experiments will be summarized using descriptive statistics for pregnant and non-pregnant women, as will the unbound RDV concentrations (calculated as follows: total concentration x free fraction) and the Albumin and AAG concentrations.

For lactating women meeting breast milk collection criteria, the number and percentage of women with detectable maternal breast milk concentrations for RDV and GS-441524, and the breast milk/plasma ratios, will be calculated and summarized using descriptive statistics. Timing of breast milk and plasma sample collection since EOI will also be summarized.

All analyses will include all participants with evaluable data for that analysis (see Section 10.2 for the definition of PK-unevaluable. For the safety analyses, a participant will only be deemed unevaluable if she does not receive any amount of RDV.

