Handling of interc		Handling of missing data	
the estimand: 1. Death This intercurrent a composite ever A supplementary principal stratum	ercurrent event is relevant to event will be addressed using at approach. analysis that applies a approach for maternal death elevant outcome measures.	Missing data will be handled using an "available case" approach. Outcome measures for participants who discontinue follow-up before the time point of interest (i.e., 7 days post-last infusion/4 weeks post- last infusion) and did not have an event of interest will be missing (i.e., these participants will not be included in the denominator).	

	As a sensitivity analysis, we will use multiple imputation over a range of potential probabilities, including "best case" (i.e., probability of event = 0) and "worst case" (i.e., probability of event = 1) scenarios.
Population-level summary measure	Analysis approach
(A) Probability of a non-pregnant women of childbearing potential, who received any amount of RDV for the treatment of COVID-19, having at least one adverse event (renal/hepatic/hematologic of any grade) through 7 days post last infusion	 (A) Proportion of participants with at least one adverse event (renal/hepatic/hematologic of any grade) through 7 days post last infusion, bounded by an exact 95% Cl (B) Proportion of participants with at least one adverse event (Grade 3 or higher/serious/
(B) Probability of a non-pregnant women of childbearing potential, who received any amount of RDV for the treatment of COVID-19, having at least one adverse event (Grade 3 or higher/serious/ Grade 3 or higher assessed as related by the CMC) through 4 weeks post last infusion	Grade 3 or higher assessed as related by the CMC) through 4 weeks post last infusion, bounded by an exact 95% Cl

6 Report Contents

This section lists the major report contents for the Primary Analysis Report. Detailed descriptions of the content of each of the following sections are given in the AIP.

- 1 Introduction
- 2 Background
 - I. Study Design
 - II. Objectives
 - III. Outcome Measures
- **3** Study History and Monitoring History
- 4 Statistical Considerations
 - I. General Considerations
 - II. Estimands and Estimation
- 5 Disposition
 - I. CONSORT Diagram
 - II. Accrual
 - III. Evaluability
- 6 Baseline Characteristics
- 7 Study Status and Retention
- 8 Status of Drug under Study and Hospitalization
- 9 Primary Analyses [Arm 1]
 - I. Non-compartmental PK Outcome Measures

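### Protocol Section 4.7 requires no final evaluations for any early exit, so a woman discontinued on safety or best-interest grounds, or withdrawing only from sampling, can lose her 4-week and delivery safety outcomes

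*Protocol*

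**What the plan says.** Protocol Section 4.7 allows voluntary withdrawal and lists four circumstances in which the site may discontinue a participant. The first, for which the Clinical Management Committee (CMC) must be consulted, is: "Investigator or designee determines that continued participation in the study would be unsafe or otherwise not in the best interest of the participant". The others are closure of the study, closure of the site, and not starting RDV within 7 days of entry. For all of them the reason must be documented, and then: "No final evaluations are required in the case of early study discontinuation or withdrawal".

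Section 6.7 treats stopping the drug differently. PK sampling ends, but "These women will be followed for safety and clinical outcomes throughout the duration of the study follow-up period".

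On data sources, Section 6 says: "With the exception of PK sampling, study procedures will largely be done via medical chart abstraction and/or remote contact or telemedicine visit". Section 6.1 says: "All information should be obtained based on available medical records or remote or telemedicine visit".

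On what is needed, the second primary objective (Section 2.1) is to "Describe the clinical and laboratory safety outcomes through four weeks post-last infusion and during delivery in pregnant women receiving RDV". Section 9.6 says: "For the safety analyses, a participant will only be deemed unevaluable if she does not receive any amount of RDV".

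On missing data, SAP Section 5.2.2 uses an available-case approach. "Outcome measures for participants who discontinue follow-up before the time point of interest" are set to missing if no event of interest has yet occurred, and those women leave the denominator. Section 5.1.2 says the same for Arm 1 and treats missing labor/delivery outcomes as missing completely at random. Both sections plan multiple imputation running from a best case (event probability 0) to a worst case (probability 1). Section 5.1.3 excludes infants of women who left before delivery, makes the same missingness assumption, and plans no sensitivity analysis.

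**The concern.** Section 4.7 does not separate the reason for leaving from what must stop. The study's only procedures on the participant are research blood samples and optional breast milk samples; the other data are taken from records or obtained remotely. A judgment that participation is unsafe therefore bears mainly on sampling. It need not end the reading of a chart. The same holds for a woman who wants no more blood drawn but does not mind her record being read: nothing in 4.7 prompts the site to ask her.

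Outcomes that may go uncollected are later Grade 3 or higher events, serious events, pregnancy outcome and birth measurements. Arm 1 safety is a primary objective with a target of about 20 women, so each woman is 1/20 = 5 percentage points. A safety-based exit reflects the participant's condition, which is difficult to reconcile with missing completely at random. It also works against the retention aim in Section 4.6 and the SAP's remark in 5.1.3 that the trial is designed to keep missing data infrequent.

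**Working it through.** **Inputs.** N = 20 with 4 events (20%) and a stated exact 95% CI of 6-44% (Protocol Section 9.4.1, Table 10; SAP Section 2.4, Table 2). Initial enrollment limit 25 per arm (Protocol 9.4.2); the 20% allowance there is for PK unevaluability, not for loss from safety follow-up. The number of women lost, k, is an assumption because the documents give none.

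**Formula.** Clopper-Pearson for x events in n women: lower limit = 2.5% quantile of Beta(x, n-x+1); upper limit = 97.5% quantile of Beta(x+1, n-x).

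**Step 1, the plan's own figure.** x = 4, n = 20 gives 20.0% (5.7-43.7%), which rounds to the stated 6-44%. All 18 rows of the table reproduce to rounding.

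**Step 2, available-case estimate.** Suppose 4 of 20 women would have an event under full follow-up, and k leave before any event of interest.

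| k lost | All k would have had an event: (4-k)/(20-k) | None would have: 4/(20-k) |
|---|---|---|
| 0 | 4/20 = 20.0% (5.7-43.7%) | 4/20 = 20.0% (5.7-43.7%) |
| 1 | 3/19 = 15.8% (3.4-39.6%) | 4/19 = 21.1% (6.1-45.6%) |
| 2 | 2/18 = 11.1% (1.4-34.7%) | 4/18 = 22.2% (6.4-47.6%) |

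With 25 women and 5 events, the starting point is 5/25 = 20.0% (6.8-40.7%). Losing one gives 4/24 = 16.7% (4.7-37.4%) or 5/24 = 20.8% (7.1-42.2%).

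**Step 3, the planned sensitivity analysis.** The best-to-worst range has width k/N: 1/20 = 5 points or 2/20 = 10 points. With one woman lost and 3 events observed, it runs from 3/20 = 15% to 4/20 = 20%; with 4 observed, from 4/20 = 20% to 5/20 = 25%. It contains the full-follow-up value but cannot say where in the range it lies.

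**Step 4, newborn measurements.** For birth weight, length and head circumference there is no corresponding bracket. The infant is left out, and SAP 5.1.3 plans nothing further.

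**Step 5, is the gap closed elsewhere?** Section 6.7 covers stopping RDV, not leaving the study. Sections 6.5 and 6.6 set out follow-up for women who remain on study. No section asks for record abstraction after an exit under the first bullet of 4.7.

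**The case against.** The strongest reply is that the protocol already deals with most women who cannot be sampled, and does so without removing them. Section 6.8.1 limits or omits PK draws when blood-volume limits would be reached. Sections 6.4.2 and 6.5.1 allow single samples to be omitted when circumstances do not permit. Sections 6.4.1 and 6.5.2 allow the milk sample to be omitted if the woman is too sick. Section 4.6 asks for every effort at retention, and a first-bullet exit needs CMC consultation. This stands. A reader might infer that women too ill for further draws are routinely taken off study; the documents do not support that. What remains is a small residual group.

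Other stronger readings also fail:

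- **Risk lasting many months.** Scheduled sampling ends about 48 hours after the last infusion, apart from delivery samples when RDV was given within 5 days. A sampling-related removal is therefore plausible for days. The consequence can still reach delivery, but Section 6.5 collects nothing between the safety and delivery periods unless Table 6 specifies it.
- **Event rates biased downward.** The shift can go either way, and events recorded before exit still count.
- **A ban on collection.** Section 4.7 says evaluations are not required. A site may still collect them, but this is left to each site.
- **Chart reading alone suffices.** After discharge, the 4-week data may need remote contact.
- **All exits should change.** A woman who never receives RDV has no last infusion and is outside the safety set. After closure of a study or site, the investigator may be unable to continue. The present rule is reasonable for both.

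Best/worst-case imputation does disclose the uncertainty for binary outcomes. It does not replace an outcome that may be in the record, and it does not extend to the newborn measurements.

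**Conclusion.** The point holds in a limited form. For women discontinued under the first bullet of Section 4.7, and for women who mean to withdraw only from sampling, the protocol permits loss of primary safety outcomes that records or remote contact could supply. In the first group the loss is related to the woman's condition, so the SAP's missing-completely-at-random assumption does not fit.

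The size depends on an unstated and probably small number of exits. If one of 20 women is lost before any event, 20% (6-44%) becomes 16% (3-40%) or 21% (6-46%). These intervals overlap heavily, so no conclusion would turn on one such loss alone. No sample-size or precision figure in the documents is wrong. This is a cheap improvement in data capture, not a defect that threatens the study. Whether consent permits abstraction after discontinuation could not be checked, because the consent form was not available.

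**What to change.** Amend Section 4.7 as follows.

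1. **First bullet only, for women who received RDV and where consent permits:** stop study sampling (blood and milk), but continue record abstraction, with remote contact if she agrees, through 4 weeks post-last infusion (Table 5) and, in Arm 1, delivery (Table 6).
2. **Voluntary withdrawal:** ask the woman or her legally authorized representative whether it covers sampling only or also record abstraction. Record the answer and abstract where permitted.
3. **Study closure, site closure, and women who never start RDV:** leave the rule as it is.

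The cost is a little extra abstraction for very few women, a protocol wording change, and possibly a consent wording change. No in-person visits or study procedures are added.

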5 DRUG UNDER STUDY

No study drug is provided as a part of this study. The drug being evaluated in this study is remdesivir (RDV) (GS-5734TM) and is referred to as the "drug under study." RDV will not be supplied as part of this study. RDV is approved by the FDA and is expected to be accessed by hospitals via existing drug distribution pathways external to the study and will be administered by the treating physician consistent with the prescribing information.

The RDV Prescribing Information is available at: https://www.gilead.com/-/media/files/pdfs/medicines/covid-19/veklury/veklury_pi.pdf

5.1 Remdesivir Formulations

RDV is available in two different formulations: lyophilized powder for reconstitution (100 mg) and premixed injection solution 5mg/mL (100 mg). RDV should be stored consistent with details as provided by the non-study sources who supply the drug to the participants. The formulation administered to each participant at each infusion will be captured on eCRFs as described in Section 6.4.

